8.2 STATISTICAL ANALYSES

8.2.1 PATIENT CHARACTERISTICS

Descriptive statistics on available patient characteristics (e.g. age, BMI, smoking, history of relevant medical diagnoses) will be reported for all exposure groups at index date. A summary table will present and compare all the patients' demographic data at index date (BZA/raloxifene/bisphosphonates).

- Age (years): derived by difference between the year of time of interest and year of birth.
- Weight (kg): recorded at the given date, or if not available, at the most recent date before or it
- Height (cm): the value at the given date or, if not available, at the most recent date before or after it.

- Body Mass Index (BMI) (kg/m^2), calculated from weight and height as defined previously. BMI will be described in quantitative measure and in categorical data, as usual
- Alcohol use
- Smoking status
- Time since diagnosis of osteoporosis: derived by the difference between the index date and the diagnosis date.
- Previous treatment for osteoporosis (before index date) (yes versus no) or Number of different treatments for osteoporosis in the entire patient history available
- Previous history of VTE (Venous Thromboembolic Events) (before index date)
- Previous history of major lower extremity (hip, knee) arthroplasty, arthroscopic surgery (information on arthroscopic surgery not available in Italian database)
- General surgery, major orthopedic surgery (<1month prior to incidence of VTE) (information on general surgery not available in Italian database)
- Multiple trauma, (<1month prior to incidence of VTE)
- Hip, pelvis, or leg fracture (<1month prior to incidence of VTE)
- Stroke (<1month prior to incidence of VTE)
- Acute spinal cord injury (paralysis) (<1month prior to incidence of VTE)
- Hormone replacement therapy (limited information available in both databases)

If the diagnoses for any of the conditions listed in this section (8.2.1) are not found in the database, they will be assumed to be absent.

8.2.2 INCIDENCE RATES

Incident rates of all primary and secondary endpoints for all three cohort groups (BZA/raloxifene/bisphosphonates) and 95% CI will be presented. The Hazard Ratio (HR) from Cox proportional hazard regression models will be used for comparison of event rates of the primary and secondary endpoints in BZA vs. bisphosphonate and BZA vs. raloxifene. A likelihood ratio test will test the null hypothesis of no difference in hazards in each pair-wise comparison. Statistical tests will use an alpha-level of 0.05.

The cumulative drug exposure of each treatment cohort will be categorized (1-30days/31-90 days/91-180 days) and used to evaluate whether or not the incidence rate of the primary and secondary end points varies with increased duration of treatment.

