### **6. STUDY PROCEDURES**

#### **6.1. Follow up time and drug exposure time**

##### **6.1.1. Follow up:**

Each woman will be followed for identification of the selected endpoints for a period of up to five years from the date of the index prescription record for bazedoxifene, raloxifene or a bisphosphonate. The follow up will continue even if the woman discontinues the index medication or switches to a different medication during the five year period.

The follow up duration of an individual woman may be shorter than the five year period if the woman transfers out of her GP office that wrote the index prescription, or if the database records the death of the woman. In these situations the data will be censored on the date of transfer or the date of death.

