##### **6.1.2. Drug exposure:**

Exposure to the drugs under study will be ascertained by searching the prescription records for the relevant product codes. For each prescription the duration of exposure will be

estimated based on the dose and quantity of the prescribed medication. For each prescription, person-time exposed to the drug will begin to accrue from the date of the prescription. The follow up time will be categorized into:

- **Current exposure:** defined as the duration of the prescription
- **Recent exposure:** defined as the 60-day period following the end of the duration of prescription
- **Past exposure:** defined as any follow up time accrued after 60 days following the end of the duration of the prescription.

A sensitivity analysis will be conducted with a different definition of exposure categories (e.g., using a 90-day window to define recent exposure).

Given the discontinuous nature of osteoporosis medication use, it is likely that a large number of women in this study will accrue ‘current use’, ‘recent use’ and ‘past use’ exposure time to multiple osteoporosis drugs during the 5-year period of follow up.

Drug exposure will also be categorized with respect to the cumulative exposure to each drug (e.g., 0-days, 1-30-days, 31-90-days, 91-180-days, 181-365-days, >365-days) to evaluate whether or not the incidence (hazard) of a specific adverse event varies with increased duration of use.

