### 7.1. Sample Size Calculation

There is no active de novo patient enrollment in this study and all women in the database who meet the inclusion criteria during the recruitment period will be included in the analysis. Therefore, the focus of the sample size calculation was to determine the precision of the estimated incidence rate ratios (IRR) that can potentially be achieved in the study depending on several different hypothetical scenarios of subject accrual. Depending on drug uptake in the participating countries, speed of accrual, event rates, and actual dropout rates, the precision of the estimated incidence rate ratio may change.

The estimates are based on the expected incidence rate of VTE as the primary endpoint. It is estimated that the incidence rate of VTE in women who are not treated with a SERM or HT is 1.74/1000 patient-years (PY), based on data from the placebo groups in bazedoxifene clinical trials. It is assumed that women treated with raloxifene would have a higher incidence of VTE, of 2.17/1000 PY, based on data from the Phase III pivotal trials of bazedoxifene. The rate of VTE observed in the raloxifene arm of the bazedoxifene pivotal trials is lower than the rate reported in the Multiple Outcomes of Raloxifene Evaluation (MORE) trial [1]. In the MORE trial, the incidence rate of VTE was 3.5/1000 patient-years in women randomized to raloxifene. Therefore, our calculations are likely to be substantially more conservative than estimates based on rates in the literature.

All estimates (Table 3, Table 4) were calculated with two-sided 95% confidence intervals. According to the study plan, there will be a 3-year accrual period and each woman will be followed for up to 5 years from enrollment. Since osteoporosis therapies are chronic therapies, it is likely that women will be exposed to the drugs for more than one year. A conservative annual loss to follow up rate of 15% was used in the estimation. Estimates were based on Wald 95% confidence intervals [2]

**Table 3: 95% Confidence Intervals (CI) for Incidence Rate Ratios (IRR) with different numbers of patients in the BZA arm and the primary comparator arm**

Bazedoxifene (n)	Bisphosphonate (n)	BZA:Bisphosphonate	Underlying Incidence Rate Ratio (IRR)		
			1	1.5	2
			95% CI of observed point estimate of IRR		
2150	8600	1:4	0.6, 1.7	1.0, 2.4	1.3, 3.0
2000	8000	1:4	0.6, 1.8	0.9, 2.4	1.3, 3.1
1750	10,500	1:6	0.6, 1.8	0.9, 2.5	1.3, 3.1
1500	12,000	1:8	0.5, 1.9	0.9, 2.5	1.3, 3.2

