8.1.3 SENSITIVITY ANALYSIS

For each prescription, duration of drug exposure will begin to accrue from the date of the prescription. The duration of drug exposure will be categorized into:

- ***Current exposure:*** defined as the duration of the prescription
- ***Recent exposure:*** defined as the 60-day period following the end of the duration of prescription
- ***Past exposure:*** defined as any follow up time accrued after 60 days following the end of the duration of the prescription.

Given the discontinuous nature of osteoporosis medication use, it is likely that a large number of women in this study will accrue 'current exposure', 'recent exposure' and 'past exposure' exposure time to multiple osteoporosis drugs during the 5-year period of follow up.

A sensitivity analysis will be conducted that compares using a 30-day and a 90-day definition of recent exposure with using the 60-day definition.

Exposure to the drugs under study will be ascertained by searching the prescription records for the relevant product codes. For each prescription the duration of exposure will be estimated based on the dose and quantity of the prescribed medication. For patients that switch treatment, the as-treated (AT) approach will be used in calculating the exposure time (see section below on patients switching treatment for more details).

There will be rules for handling missing values of dose or quantity prescribed in Italian and Spanish LPD databases. In LPD databases, the number of days of supply or daily

dose is not recorded by some GPs in Spain and Italy. If duration is not available, the number of days of supply will be calculated by dividing total number of pills (number of prescribed box times number of pills in a box) by the daily dose. If duration and daily dose are not available, the number of days' supply will be calculated by dividing total number of pills (number of prescribed box multiplied by the number of pills in a box) by the standard dose/recommended dose.

Drug exposure will also be categorized with respect to the cumulative exposure to each drug (e.g., 0-days, 1-30-days, 31-90-days, 91-180-days, 181-365-days, >365-days) to evaluate whether or not the incidence (hazard) of a specific adverse event varies with increased duration of use.

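### SAP 8.2.2 stops the cumulative-exposure bands at 180 days and omits the 181-365 and >365-day bands that SAP 8.1.3 and protocol 6.1.2 list for the same duration-of-use analysis

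*SAP*

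**What the plan says.** The cumulative-exposure variable is described in three places.

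- Protocol 6.1.2 and SAP 8.1.3 give the same six bands, as examples: "e.g., 0-days, 1-30-days, 31-90-days, 91-180-days, 181-365-days, >365-days". The stated aim is to see whether the hazard of an adverse event changes with longer use.
- SAP 8.2.2 says: "The cumulative drug exposure of each treatment cohort will be categorized (1-30days/31-90 days/91-180 days"). This list is not offered as an example. It has no band above 180 days and no 0-day band. The bands are to be "used to evaluate whether or not the incidence rate of the primary and secondary end points varies with increased duration of treatment".

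Two statements bear on how much use lies beyond 180 days. Protocol 6.1.1 follows each woman "for a period of up to five years from the date of the index prescription record". Protocol 7.1 says "it is likely that women will be exposed to the drugs for more than one year". On the other side, protocol 6.1.2 begins one sentence with "Given the discontinuous nature of osteoporosis medication use", and neither document gives a persistence figure.

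**The concern.** The same variable, serving the same question, has two definitions within one SAP. The section that commits to specific analyses carries the shorter one. The question is whether incidence changes with increasing duration of treatment, and the missing bands cover use from six months upward. SAP 8.1.2 describes the endpoints as chronic diseases or malignancies with potentially long latency, so longer use is the range of most interest.

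A programmer who follows 8.2.2 would produce tables that stop at 180 days. One who follows 8.1.3 would choose among bands given only as examples, possibly with the data in hand. Either way, the SAP has not fixed the analysis.

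**Working it through.** **Side by side**

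| Source | 0 d | 1-30 d | 31-90 d | 91-180 d | 181-365 d | >365 d | Status |
|---|---|---|---|---|---|---|---|
| Protocol 6.1.2 | yes | yes | yes | yes | yes | yes | example list |
| SAP 8.1.3 | yes | yes | yes | yes | yes | yes | example list |
| SAP 8.2.2 | no | yes | yes | yes | no | no | stated list |

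No other SAP text settles the difference. The amendment table (SAP 1) records administrative and template changes only, the summary of analyses (8.2.5) names no cumulative-exposure bands, and table shells (SAP 9) are marked not applicable.

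**How much on-drug time would have no band**

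The documents state no such share, so there is no planned figure to reproduce.

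*Bound without a model.* No woman can contribute more than 180 days to the three bands. The share of on-drug time beyond 180 days is therefore at least 1 - 180/(mean days on drug). Reading protocol 7.1 as a mean above 365 days gives 1 - 180/365 = 0.507, so at least about 51%, whatever the distribution.

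*Range under a model.* Inputs:
- five-year cap (protocol 6.1.1);
- annual loss: "A conservative annual loss to follow up rate of 15% was used in the estimation" (protocol 7.1), which gives a hazard of -ln(0.85) = 0.1625 per year;
- exponential discontinuation with median persistence m, an assumption, which adds ln 2/m per year.

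With λ the sum of the two hazards and 180 days = 0.493 years:
- on-drug years per woman = (1 - exp(-5λ))/λ;
- of which in the first 180 days = (1 - exp(-0.493λ))/λ;
- share beyond 180 days = 1 - (1 - exp(-0.493λ))/(1 - exp(-5λ)).

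| Assumed median persistence | λ per year | On-drug years | In first 180 d | Share beyond 180 d |
|---|---|---|---|---|
| 3 months | 2.935 | 0.34 | 0.261 | 24% |
| 6 months | 1.549 | 0.65 | 0.345 | 47% |
| 1 year | 0.856 | 1.15 | 0.402 | 65% |
| 2 years | 0.509 | 1.81 | 0.436 | 76% |
| No discontinuation | 0.1625 | 3.42 | 0.474 | 86% |

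With no loss to follow-up the shares are 26%, 50%, 70%, 81% and 90%. The share reaches one half at a median persistence of about 180 days without loss, or about 204 days with 15% annual loss. In the two rows below one half, mean on-drug time is under one year, contrary to the protocol's expectation.

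**Why no single event figure follows**

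Take 1,823 bazedoxifene women (SAP 5.4), the protocol 7.1 rate for women not on a SERM or hormone therapy, which "is 1.74/1000 patient-years (PY"), an incidence rate ratio of 1 and 15% annual loss.

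- *On-drug time only.* Expected VTEs in the first 180 days = 1,823 × 0.00174 × years in the first 180 days. At 1-year persistence this is 1.3 of 3.7 on-drug events; with no discontinuation, 1.5 of 10.9.
- *All follow-up, as in the ever-exposed person-time of SAP 8.1.2.* A woman who stops before 180 cumulative days stays in a listed band afterwards. Follow-up is 3.42 years per woman. The part with more than 180 days of use is exp(-0.493 × ln 2/m) × (exp(-0.493 × 0.1625) - exp(-5 × 0.1625))/0.1625. At m = 1 year this is 0.711 × 2.949 = 2.10 years, or 61%, leaving 1.33 years in band and about 4.2 of 10.9 VTEs. At 2 years and 6 months, 73% and 44% lie outside, with about 3.0 and 6.1 VTEs in band.
- *Hazard not constant.* With on-drug time and 1-year persistence, the share of VTEs after 180 days is 65% under a constant hazard. It falls to 48%, 38% or 27% if the hazard in the first 180 days is 2, 3 or 5 times the later one (assumed multiples).

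**The case against.** - *The full list is still in the SAP.* Section 8.1.3 keeps all six bands, and nothing ranks 8.2 above 8.1. This stands in part: the loss occurs only if 8.2.2 is followed. It does not remove the contradiction.
- *The SAP may depart from the protocol.* Protocol 7 allows this, so the difference from the protocol alone is not an error. The SAP's disagreement with itself remains, and no reason for shorter bands is given.
- *Other analyses look at change over time.* SAP 8.1.4 tests proportional hazards, explores time-varying hazard ratios where the assumption fails, and runs an as-treated analysis with time-dependent exposure. This stands: it would be wrong to say the study as a whole cannot examine risk beyond six months. These analyses do not tabulate incidence by cumulative use, which is what the bands are for.
- *A reader might infer that most on-drug time and most VTEs have no band.* The documents do not establish that. The first fails if median persistence is below about six to seven months, and the protocol itself calls use discontinuous. The second also needs an assumption about the hazard over time, which is what this analysis is meant to test, and a rule on off-drug time.
- *The analysis is supportive and sparse.* With about 11 bazedoxifene VTEs expected even with no discontinuation, any banding will be imprecise. This stands, and it limits the weight of the point for VTE.

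**Conclusion.** The point holds as an internal contradiction with a clear consequence. SAP 8.2.2 leaves out the 181-365 and >365-day bands, and the banded analysis run from it could not describe incidence beyond 180 cumulative days. The on-drug time without a band is at least about 51% if mean exposure exceeds one year, and 24% to 86% across the assumed persistence range with 15% annual loss. These shares rest on assumed persistence and on 8.2.2 being the text that is followed. The share of VTEs affected cannot be fixed from the documents and should not be quoted as one number. The correction is worth making before analysis because it is nearly free.

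**What to change.** In SAP 8.2.2, add the 181-365 and >365-day bands so that the list agrees with SAP 8.1.3 and protocol 6.1.2, and apply it to all primary and secondary endpoints. State the list as fixed in both SAP sections, not as an example. A 0-day band is needed only where exposure to drugs other than the index drug is tabulated: SAP 2.1 requires at least one prescription for entry, so that band is empty for a cohort's own index drug.

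Cost: one line of text and two more table rows per endpoint. No new data are needed. VTE counts per band will be small and should be presented as such.

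### The cumulative-exposure bands in SAP 8.2.2 stop at 180 days and conflict with the open-ended bands in SAP 8.1.3 and protocol 6.1.2

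*SAP*

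**What the plan says.** SAP 8.2.2 (Incidence Rates) states that the cumulative exposure of each treatment cohort "will be categorized (1-30days/31-90 days/91-180 days". The purpose is to see whether the rate of the primary and secondary endpoints "varies with increased duration of treatment". The list is closed: nothing marks it as an example, and there is no top category.

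SAP 8.1.3 (Sensitivity Analysis) describes cumulative exposure to each drug for the same purpose, with the bands given as "e.g., 0-days, 1-30-days, 31-90-days, 91-180-days, 181-365-days, >365-days". Protocol 6.1.2 has the same list: "Drug exposure will also be categorized with respect to the cumulative exposure to each drug (e.g., 0-days, 1-30-days, 31-90-days, 91-180-days, 181-365-days, >365-days".

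Two other statements set the time scale. Protocol 6.1.1 follows each woman "for a period of up to five years from the date of the index prescription record", and follow-up continues after she stops or switches. Protocol 7.1 calls these chronic therapies and says "it is likely that women will be exposed to the drugs for more than one year".

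**The concern.** An analysis of whether risk changes with longer use needs categories for longer use. The 8.2.2 list covers the first six months of exposure and then ends. A programmer working from 8.2.2 would have no cell for a woman once her cumulative exposure passes 180 days. One working from 8.1.3 would have two further cells, 181-365 days and above 365 days. The results reported for the same stated question would differ.

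What is at stake is the ability of this analysis to show a risk that persists or appears late. That matters here because the endpoints include malignancies, and SAP 8.1.2 itself refers to potentially long latency.

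**Working it through.** **Step 1. The lists side by side.**

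| Band (days) | Protocol 6.1.2 | SAP 8.1.3 | SAP 8.2.2 |
|---|---|---|---|
| 0 | yes | yes | no |
| 1-30 | yes | yes | yes |
| 31-90 | yes | yes | yes |
| 91-180 | yes | yes | yes |
| 181-365 | yes | yes | no |
| >365 | yes | yes | no |
| Given as an example | yes | yes | no |

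The six-band list covers every possible value up to five years. The three-band list covers 1 to 180 days only. The missing upper bands are the material part. A woman enters a cohort through a prescription for its drug, so a 0-day band has members mainly when exposure is counted per drug across switches, as 8.1.3 does.

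**Step 2. Does anything resolve the difference?** The summary of analyses in SAP 8.2.5 does not mention cumulative-exposure bands. SAP section 1 reports only administrative and format changes for version 2.0. SAP section 9 gives no table shells. No reason for shorter bands appears anywhere.

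**Step 3. Calendar follow-up after day 180.** The documents state no figure to reproduce, so this is a check of scale. Inputs are five years of follow-up (protocol 6.1.1) and the loss rate in protocol 7.1: "A conservative annual loss to follow up rate of 15% was used in the estimation". I treat loss as a constant hazard.

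- h = -ln(0.85) = 0.1625 per year; t = 180/365.25 = 0.493 years.
- Expected follow-up over five years: (1 - 0.85^5)/h = 0.5563/0.1625 = 3.42 person-years per woman.
- Expected follow-up in the first 180 days: (1 - 0.85^0.493)/h = 0.0770/0.1625 = 0.47 person-years.
- Share after day 180: 1 - 0.47/3.42 = 86%. With no loss it is 1 - 0.493/5 = 90%.

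**Step 4. Follow-up with cumulative exposure above 180 days.** The bands measure exposure, not calendar time. A woman who stops after 100 days stays in the 91-180 band for the rest of her follow-up. Persistence is not given, so I assume one-year persistence p, continuous use until stopping, a constant stopping hazard, and stopping independent of loss. The proportion still on drug at day 180 is then p^0.493, and the share is 0.862 × p^0.493.

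| Assumed p | 80% | 60% | 50% | 40% | 30% | 20% |
|---|---|---|---|---|---|---|
| Share of follow-up above 180 days' exposure | 77% | 67% | 61% | 55% | 48% | 39% |

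The share passes one half when p exceeds (0.5/0.862)^(1/0.493), about 33%. With no loss the threshold is about 30%.

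**Step 5. Expected events.** With 1,823 bazedoxifene women (SAP 5.4), 1.74 VTE per 1000 person-years (protocol 7.1) and a rate ratio of 1, the expected count is 1823 × 3.42 × 0.00174, about 10.9. About 1.5 fall in the first 180 calendar days and 9.4 later. Some of the later events would occur in women whose cumulative exposure never passed 180 days.

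**The case against.** The strongest reply is that this is a truncated restatement, not a decision. The long bands stand in the methods section of the same SAP with the same aim, no rule gives 8.2 precedence over 8.1, and the six-band lists are examples, so exact cut-points were never fixed. Most of this stands. A reader might infer that the SAP omits long exposure altogether, but 8.1.3 shows otherwise: the defect is an unresolved conflict. The example wording leaves cut-points open, but does not explain a closed list that ends at 180 days.

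A second reply is that late risk can be seen elsewhere. SAP 8.1.4 plans cumulative-risk analyses that carry the initial cohort forward through follow-up, and time-varying hazard ratios where proportional hazards fails. That stands for time since the index prescription. It does not replace an analysis by amount of drug taken, which is what 8.2.2 sets out to do.

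A third reply is that about 11 expected bazedoxifene VTEs, spread over six bands, support description only. That is fair, but it is no reason to leave the later events without a band.

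Three stronger readings are tempting and are not supported:

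- That 86% of drug exposure is lost. The 86% is calendar follow-up. It would apply to cumulative exposure only if nobody stopped treatment, and both documents stress that use is discontinuous.
- That the protocol expects most women to be treated for more than a year. Protocol 7.1 says only that such exposure is likely, and gives no proportion.
- That the analysis will create a spurious falling trend, because early events land in short bands when women are classified by final total exposure. The SAP does not state that method. It is silent on time-updating of cumulative exposure. What it does say leans the other way: exposure accrues from each prescription date, and the as-treated analysis in 8.1.4 assigns each event to the treatment at that time.

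**Conclusion.** The conflict is real, and 8.2.2 is wrong as written for its stated purpose: it has no band for cumulative exposure beyond 180 days in an analysis of longer treatment. That conclusion comes from comparing the texts and rests on no assumption. Its size does. About 86% of calendar follow-up lies after day 180 under a constant 15% annual loss. The share of follow-up with cumulative exposure above 180 days is about 39% to 77% for one-year persistence of 20% to 80%, under the assumptions in step 4.

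The reach is limited to the supplementary duration-response analysis. The primary comparison of bazedoxifene with bisphosphonates, the significance level and the sample-size reasoning are untouched.

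**What to change.** Replace the list in SAP 8.2.2 with the six bands of SAP 8.1.3 and protocol 6.1.2: 0, 1-30, 31-90, 91-180, 181-365 and >365 days, keeping the open top category. If shorter bands were intended, say so in 8.2.2 and give the reason.

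As a clarification, add one sentence saying that person-time and events are assigned to the cumulative-exposure band reached at that time. A time-dependent exposure term in the Cox model is not needed to resolve the conflict.

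The cost is SAP wording only. The prescription data are already planned for in 8.1.3, and no protocol change is needed because the protocol already has the fuller list. The change should be made before the final analysis.
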